## 1 SYNOPSIS

STUDY No:	GER-CAD-19-11180														
TITLE	Thromboembolic Risk and Mortality of Patients with Cold Agglutinin Disease (CAD) in European Countries: A Retrospective Chart Review														
LOCATION	EU countries: Germany, Italy, Austria														
STUDY OBJECTIVES AND OUTCOMES	To better understand thrombotic events (TEs) and mortality in CAD														
	
  
 Objectives	Outcomes	
   
 Primary	
 
  
 
To estimate incidence rates of thrombotic events (TEs) in CAD
 
 	 
 
Crude incidence rate of TE (overall and by type)
 
 	
 
 Secondary	
 
  
 
To characterize TEs in CAD and the risk factors for developing TE in CAD
 
 	 
 
Analysis of thromboembolic complications in patients with CAD: 
 
Incidence rate of TE by type (arterial, venous) after CAD diagnosis
 
Cumulative incidence of TE after CAD diagnosis
 
Correlation between CAD-clinical severity and TE occurrence
 
 
 
 	
 
  
 
To estimate mortality rates in CAD; all-cause, and by underlying cause
 
 	 
 
OS (Overall Survival) in CAD / mortality rate: 
 
Mortality rate in CAD, all cause and cause-specific mortality
 
Overall survival
 
 
 
 	
 
  
 
To assess health care resource utilization (HCRU) associated with TEs in CAD
 
 	 
 
Direct Health care resource utilization (HCRU) associated with TE in CAD: 
 
Percentage of patients with TE-related inpatient hospitalizations, ER, ICU and outpatient visits
 
Length of stay of inpatient hospitalizations related to TEs
 
Number of procedures / surgeries associated with TE diagnosis and management
 
 
 
 	
  
	Objectives	Outcomes	Primary		
 
To estimate incidence rates of thrombotic events (TEs) in CAD
 
	
 
Crude incidence rate of TE (overall and by type)
 
	Secondary		
 
To characterize TEs in CAD and the risk factors for developing TE in CAD
 
	
 
Analysis of thromboembolic complications in patients with CAD: 
 
Incidence rate of TE by type (arterial, venous) after CAD diagnosis
 
Cumulative incidence of TE after CAD diagnosis
 
Correlation between CAD-clinical severity and TE occurrence
 
 
 
	
 
To estimate mortality rates in CAD; all-cause, and by underlying cause
 
	
 
OS (Overall Survival) in CAD / mortality rate: 
 
Mortality rate in CAD, all cause and cause-specific mortality
 
Overall survival
 
 
 
	
 
To assess health care resource utilization (HCRU) associated with TEs in CAD
 
	
 
Direct Health care resource utilization (HCRU) associated with TE in CAD: 
 
Percentage of patients with TE-related inpatient hospitalizations, ER, ICU and outpatient visits
 
Length of stay of inpatient hospitalizations related to TEs
 
Number of procedures / surgeries associated with TE diagnosis and management
 
 
 

	Objectives	Outcomes													
Primary															

 
To estimate incidence rates of thrombotic events (TEs) in CAD
 
	
 
Crude incidence rate of TE (overall and by type)
 
														
Secondary															

 
To characterize TEs in CAD and the risk factors for developing TE in CAD
 
	
 
Analysis of thromboembolic complications in patients with CAD: 
 
Incidence rate of TE by type (arterial, venous) after CAD diagnosis
 
Cumulative incidence of TE after CAD diagnosis
 
Correlation between CAD-clinical severity and TE occurrence
 
 
 
														

 
To estimate mortality rates in CAD; all-cause, and by underlying cause
 
	
 
OS (Overall Survival) in CAD / mortality rate: 
 
Mortality rate in CAD, all cause and cause-specific mortality
 
Overall survival
 
 
 
														

 
To assess health care resource utilization (HCRU) associated with TEs in CAD
 
	
 
Direct Health care resource utilization (HCRU) associated with TE in CAD: 
 
Percentage of patients with TE-related inpatient hospitalizations, ER, ICU and outpatient visits
 
Length of stay of inpatient hospitalizations related to TEs
 
Number of procedures / surgeries associated with TE diagnosis and management
 
 
 
														
STUDY DESIGN & DURATION	This is a multinational, multicenter non-interventional study of all patients with a CAD diagnosis from January 1 st , 2009 through January 1 st , 2019 seen at hematology/oncology centers in European countries (Germany, Italy, Austria).														

Property of the Sanofi-Aventis Groupe - strictly confidential

Protocol template for disease observational studies				
			Research and Development	
QSD-003149	Disease observational study	with disease	Application Date (DD/MM/YYYY) :dd-Mmm-09/11/2020	EFFECTIVE

<DD-MM-YYYY HH:mm:ss> < 15-01-2021 21:03:21 > UTC

Formatted: Left, Tab stops: 8,89 cm, Centered + 17,1 cm, Right

primary data collection  
Study Number: GER-CAD-19-11180

Version number: ~~V6~~V7.0

	
Data from medical records from all eligible patients will be analyzed from the first relevant examination (January 2009 at the earliest) until the end of study follow-up on 1st January 2020, lost to follow-up or the patient's death. This time frame is based on consideration of a minimum time period required to achieve enrolment of the target number of patients, while excluding most recent follow-up period likely to have been impacted by the covid-19 pandemic. No visits, examinations, or procedures are mandated for this study.
 
Demographic, clinical, and laboratory data will be extracted from medical records by using predesigned case report forms. Patient data will be de-identified, but a patient number will be assigned, and an identification key will be retained at each center.
 
Informed consent will be obtained from enrolled patients allowing the use of their medical records for research (a waiver of informed consent may be obtained for deceased patients, lost to follow up patients and patients who did not visit the site during the documentation period, as per local regulations). Submissions to the respective Ethics Committees (EC)/Regulatory Authorities will be carried out in each country.
 
In all countries, two different enrolled patient identification logs will be documented: one specific log for patients who signed an informed consent form, another specific one for dead patients, lost to follow up patients and for alive patients who did not visit the site during the data collection period. At the time of the database lock, and before the analysis, the specific enrolled patient identification log documented for dead patients, lost to follow up patients and for patients who did not visit the site during the data collection period, and where the unique identifier is documented, will be destroyed. Therefore, collected data will not be identifiable for these patients.

STUDY POPULATION	
Inclusion Criteria
 
 
• Age ≥18 years
 
• An explicit cold AIHA (CAD) diagnosis in the patient medical chart between January 1st, 2009 and January 1st, 2019, based on: 
 
– Presence of chronic hemolysis
 
 
 
 
AND
 
 
– A positive direct antiglobulin test (DAT), with a typical DAT pattern of a positive monospecific test for C3d only
 
 
OR
 
 
– A positive direct antiglobulin test (DAT), with a typical DAT pattern of a weakly positive for IgG in addition to C3d
 
 
 
• Evidence of a signed and dated informed consent document indicating that the patient (or a legally acceptable representative) has been informed of all pertinent aspects of the study. A request for a waiver of informed consent for patients deceased, lost to follow up or alive but did not visit the site at time of data collection will be requested, where applicable.
 
 
As this study will be conducted in a real-world setting with treating physicians assessing CAD vs CAS, reported patients who were diagnosed with CAD but whose medical records do not capture the data required to define CAD using strict hemato-

Protocol template for disease observational studies				
			Research and Development	
QSD-003149	Disease observational study	with disease	Application Date (DD/MM/YYYY) : dd-Mmm-09/11/2020	EFFECTIVE

<DD-MM-YYYY HH:mm:ss> < 15-01-2021 21:03:21 > UTC

primary data collection  
Study Number: GER-CAD-19-11180

Version number: ~~V6~~V7.0

	
immunologic diagnosis criteria [ie High titer cold reactive antibody (CA) (most often defined as <math>\geq 64</math> at 4°C); CA with a thermal amplitude <30°C] will be included in the study and classified as "presumed CAD".
 
Exclusion Criteria
 
 
• Patient with any other form of hemolytic anemia, including CAS and mixed AIHA
 
• Presence of records of any cause of secondary CAS at diagnosis [concurrent diagnosis of any type of lymphoma, multiple myeloma, chronic lymphocytic leukemia, Waldenström macroglobulinemia, other active cancer, or recent infection with mycoplasma pneumoniae Epstein-Barr virus, cytomegalovirus, Autoimmune disorders (SLE)]
 
 
Expected number of patients: Approx. 170

RECRUITMENT MODALITIES	
Selection of sites/investigators
 
A feasibility study will be run to select study sites/investigators able to reach recruitment goals and having the infrastructure or material resources necessary for completing the chart review study. A comprehensive list of hematology and oncology hospitals potentially managing CAD patients will be approached for the feasibility study in Germany. Referral centers of CAD expertise will be contacted in Italy and Austria.
 
Selection of patients
 
Study investigators routinely involved in the management of CAD patients (or delegates at the study site) will screen medical records of their patients diagnosed with CAD between January 1st, 2009 and January 1st, 2019 in a consecutive, retrospective order and include all those who fulfil pre-defined study eligibility criteria.

MAIN DATA COLLECTED	
 
• Demographics: Date of birth (month, year); Sex
 
• Relevant medical history: Any chronic or serious disease other than CAD and diagnostic date; Risk factors for TE; Previous medical history of TE
 
• CAD characteristics: Age at onset of anemia or clinical symptoms; Age at diagnosis; Clinical presentation at or before diagnosis; Biological features at diagnosis; Transfusion history; Disease status over follow-up; History of hemolytic exacerbation/flares
 
• Thromboembolic events: Type of TE events (arterial, venous) and other events such as post-thrombotic syndrome and pulmonary hypertension, and dates
 
• Drug therapy associated with CAD: Agent/s (including any Corticosteroid Containing Therapy and Rituximab); Daily dose for corticosteroids; Duration of therapy, line of treatment; Treatment response (complete response, partial response, non-response); Splenectomy; Thromboprophylaxis
 

Property of the Sanofi-Aventis Groupe - strictly confidential

Protocol template for disease observational studies				
			Research and Development	
QSD-003149	Disease observational study protocol v. 6.0yyyy	with disease	Application Date (DD/MM/YYYY) :dd-Mmm- 09/11/2020	EFFECTIVE

<DD-MM-YYYY HH:mm:ss> < 15-01-2021 21:03:21 > UTC

Formatted: Left, Tab stops: 8,89 cm, Centered + 17,1 cm, Right

primary data collection  
Study Number: GER-CAD-19-11180

Version number: ~~V6~~V7.0

	
 
Direct HCRU associated with TE: All-cause inpatient admissions and length of stay (LOS); Outpatient visits; Admissions to ICU and LOS; Emergency room (ER) visits; Surgical and other major procedures
 
Patient vital status: Date of death; Cause of death
 

STATISTICAL METHODOLOGY	
Sample size calculation
 
The study aims to extract data from approximately 170 CAD patients from hospital chart reviews from hematology and oncology clinics offering specialized care for CAD patients in the countries of interest.
 
Given the rarity of CAD, the number of patients included in the study is expected to be small. For this reason, no hypotheses have been pre-specified and sample size calculations are not applicable.
 
The sample size is based on consideration of a minimum number of CAD patients required in terms of precision around expected TE incidence rates according to the literature.
 
Assuming a TE incidence rate of 20-30% in CAD patients and a total sample of 170 CAD patients, the margin of error in the TE subgroup will be within <math>\pm 6.0</math> and 6.9% with an <math>\alpha</math> risk of 95%.
 
Analysis
 
This study is primarily descriptive in nature and it does not include formal statistical hypothesis testing.
 
All variables will be summarized descriptively through tabular displays of mean, median, ranges and standard deviations (SD) of continuous variables and frequency distributions of categorical variables. Changes in disease activity closest to the date of each study event will be described, where data are available. Crude incidence rates (with 95% CI) will be calculated from the number of TE after CAD diagnosis and the sum of individual person-years contributed by the CAD population during the study period. The mortality rate will also be estimated in this way. For event analysis, the main events evaluated will include time to first TE and time to death. The cumulative incidence of TE will be estimated using Kaplan-Meier survival analysis accounting for mortality as a competing risk event if sample size allows it.
 
Descriptive analysis will be used to identify risk factors associated with occurrence of TE.
 
Per-patient-per-month (PPPM) HCRU, will be calculated during the variable follow-up period of up to 12 months after the TE diagnosis.
 
Both "confirmed" and "presumed" CAD patients will be included in the primary analysis. Sensitivity analyses will be performed to address any potential misclassification in CAD diagnosis.
 
An interim analysis will be performed when the documentation of two out of three countries is completed, and when minimum number of patients have been included in two countries.
 
A global report <del>and a specific report for Italy</del> will be written.


Protocol template for disease observational studies				
			Research and Development	
QSD-003149	Disease observational study	with disease	Application Date (DD/MM/YYYY) : dd-Mmm-09/11/2020	EFFECTIVE

<DD-MM-YYYY HH:mm:ss> < 15-01-2021 21:03:21 > UTC

primary data collection  
Study Number: GER-CAD-19-11180

Version number: ~~V6~~V7.0

ESTIMATED DURATION OF THE STUDY	Estimated enrollment duration: <del>10-14</del> months
	Estimated dates: end-August 2022 – <del>end-early-June</del> October 2023
	First Site Active: August 29th, 2022
	Last Site Active: <del>end-of-April</del> October 2023
	Last Data In: <del>end-of-June</del> October 2023

Property of the Sanofi-Aventis Groupe - strictly confidential

Protocol template for disease observational studies					
				Research and Development	
QSD-003149	Disease observational study	with disease	Application Date (DD/MM/YYYY) : dd-Mmm-09/11/2020	EFFECTIVE	
protoco v. 6.0yyyy					

<DD-MM-YYYY HH:mm:ss> < 15-01-2021 21:03:21 > UTC

[figure not shown]
Formatted: Left, Tab stops: 8,89 cm, Centered + 17,1 cm, Right

primary data collection  
Study Number: GER-CAD-19-11180

Version number: ~~V6~~V7.0

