### 2.2 STUDY FLOW CHART

The study consists of the documentation of an e-CRF for adult patients with CAD (please refer to Section 10.1 for details).

Note: The observational study operates under real clinical practice conditions; it collects only available data and necessary data for the purpose. There are no imposed protocol visits or procedures.

Protocol template for disease observational studies			
		Research and Development	
QSD-003149	Disease observational study with disease Application Date (DD/MM/YYYY) : dd-Mmm-09/11/2020	protoco v. 6.0/yyyy	EFFECTIVE

<DD-MM-YYYY HH:mm:ss> < 15-01-2021 21:03:21 > UTC

primary data collection

Study Number: GER-CAD-19-11180

Version number: ~~V6~~V7.0

Study Flow Chart			
Evaluation	Inclusion	Retrospective Eligibility Period: At CAD diagnosis between January 1st, 2009 – January 1st, 2019 (index date)	Retrospective Patient Follow-up: From the index date until study end (January 1st, 2020) or patient death or lost to follow-up, whichever occurs first
Informed consent form	Date of next routine consultation at the site (Italy only, for patients to sign the ICF at site as per local regulation)	Signature of the ICF prior to data collection	
Inclusion criteria	
 
Adult patients aged ≥18 years
 
Patients who fully meet the diagnostic criteria (see opposite)
 
Evidence of a signed and dated informed consent document indicating that the patient (or a legally acceptable representative) has been informed of all pertinent aspects of the study
 
	After they agree signing the informed consent form, adult patients aged ≥18 years diagnosed between January 1 st , 2009 and January 1 st , 2019 with an explicit cold AIHA (CAD) based on: 
 
Presence of chronic hemolysis
 
 AND 
 
A positive direct antiglobulin test (DAT), with a typical DAT pattern of a positive monospecific test for C3d only
 
OR
 
A positive direct antiglobulin test (DAT), with a typical DAT pattern of a weakly positive for IgG in addition to C3d
 
	

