### 7.1 DESCRIPTION OF THE STUDY DESIGN

This is a European, multicenter, observational study of all adult patients with a CAD diagnosis from January 1st, 2009 through January 1st, 2019 seen at hematology/oncology centers in Germany, Italy and Austria.

Protocol template for disease observational studies				
			Research and Development	
QSD-003149	Disease observational study	with disease	Application Date (DD/MM/YYYY) : dd-Mmm-	EFFECTIVE
	protoco v. 6.0	yyyy	09/11/2020	

<DD-MM-YYYY HH:mm:ss> < 15-01-2021 21:03:21 > UTC

primary data collection  
Study Number: GER-CAD-19-11180

Version number: ~~V6~~V7.0

This observational study plans to collect information on the thromboembolic risk and mortality in CAD patients. Data will be extracted retrospectively from the initial date of CAD diagnosis until the earliest of death, end of data availability (*i.e.* lost to follow-up) or end of data collection set on January 1st, 2020 for approximately 170 patients in total. The design of the study will mirror real life management of these patients.

Pseudo-anonymous subject-level data will be transcribed, retrospectively, from medical records onto electronic case report forms (eCRFs) by study investigators routinely involved in the management of these patients (or delegates at the study site). No examinations or procedures apart from those occurring as part of the patient's routine clinical care are required for this study.

Chart reviews will be performed regardless of whether patients are alive at the time of data collection. In order to include the maximum follow-up data available per patient, patient's medical records will be abstracted retrospectively from initial clinical manifestation of CAD until death, loss to follow-up or end of data collection, whichever comes first. There will be no prospective follow-up period.

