### 8.2 INCLUSION CRITERIA

Patients must meet all the following criteria to be eligible for the study:

- Patient aged  $\geq 18$  years
- Patient who fully meet the diagnostic criteria per section 7.1:
- Evidence of a signed and dated informed consent document indicating that the patient (or a legally acceptable representative) has been informed of all pertinent aspects of the study. A request for a waiver of informed consent for patients deceased, lost to follow up or alive but did not visit the site at time of data collection will be requested, where applicable.

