### 13.2 DISPOSITION OF PARTICIPANTS

The following data will be presented to describe the patients' disposition:

- Number and percentage of patients belonging to the analysis population.

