## 14.2 RESPONSIBILITIES OF THE INVESTIGATORS

The Investigator will perform the study in accordance with this protocol, applicable local regulations and international guidelines.

It is the Investigator's responsibility to:

- Obtain written informed consent from participants prior to inclusion in the study,
- Fill in the CRF and to record all data pertinent to the study. She/he will ensure that the information reported in the CRF is precise and accurate.

The Investigator or a person designated by the Investigator, and under the Investigator's responsibility, should fully inform the participant of all pertinent aspects of the study including the written information. All participants should be informed to the fullest extent possible about the study, in language and terms they are able to understand.

Prior to a participation in the study, the written informed consent form (ICF) should be signed, name filled in and personally dated by the participant or by the participant's legally acceptable representative, and by the person who conducted the informed consent discussion. A copy of the signed and dated written ICF will be provided to the participant.

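### A site that cannot or does not use the consent waiver can count no deaths, yet 13.3 pools it into the mortality analyses and two sections require consent with no waiver exception

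*Protocol*

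**What the plan says.** **Consent.** Section 8.2 makes this an inclusion criterion: "Evidence of a signed and dated informed consent document indicating that the patient (or a legally acceptable representative) has been informed". The flow chart (2.2) places signature before data collection and opens its eligibility text with "After they agree signing the informed consent form, adult patients aged". Section 14.2 gives the investigator the duty to "Obtain written informed consent from participants prior to inclusion in the study". Neither 2.2 nor 14.2 mentions an exception.

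**Waiver.** The Synopsis says "a waiver of informed consent may be obtained for deceased patients, lost to follow up patients and patients who did not visit the site", subject to local regulations. Section 8.2 is somewhat firmer. It says of "A request for a waiver of informed consent for patients deceased, lost to follow up or alive but did not visit the site" that the request will be made where it applies. Neither text says what happens if the request is refused. The Synopsis adds "In all countries, two different enrolled patient identification logs will be documented": one for consenting patients and one for dead, lost and non-visiting patients. Sections 10.3.3 and 16.3 repeat this. The second log is destroyed at database lock, before analysis.

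**Intended population.** Section 7.1: "Chart reviews will be performed regardless of whether patients are alive at the time of data collection". Section 8.4 expects all consecutive eligible patients to be included.

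**Dates.** The first site is active on 29 August 2022 (Synopsis, estimated duration). Data collection is closed at 1 January 2020 (10.1).

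**Analysis.** Mortality (all-cause and cause-specific) and overall survival are secondary outcomes (section 6). Section 13.3 puts every eligible, documented patient into one population. Section 13.2 reports only "Number and percentage of patients belonging to the analysis population". Section 10.3.1 expects mortality to be under-estimated because some deaths go unrecorded, and names no other cause.

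**The concern.** The protocol wants a cohort that does not depend on vital status, but it admits patients by two routes that depend on vital status completely. Deceased patients need a waiver that is not assured. Patients who sign must have survived well beyond the end of follow-up, so all of their person-time is immortal. Two sections that investigators will work from state consent with no exception, which contradicts the Synopsis, 7.1 and 8.2.

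If any site or country ends up with consent only, its mortality rate is zero because of how patients entered, not because of the disease. Pooling it lowers the mortality rate and raises overall survival, and it thins the cause-specific counts. The planned disposition line would not reveal this. Section 5.2 says the results will support HTA dossiers, so the mortality figure will be used.

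Where the waiver does operate, a smaller bias runs the other way: living attenders can refuse, while the dead cannot.

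**Working it through.** The protocol gives no figure for mortality precision or for the share of patients entering by waiver, so there is nothing of its own to reproduce on this point.

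**Step 1: dates.** From 1 January 2020 to 29 August 2022 is 731 + 240 = 971 days, or 971/365.25 = 2.66 years. Every countable death precedes the earliest possible signature by at least that long. A patient who signs therefore contributes 0 deaths and full follow-up to the cut-off.

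**Step 2: inputs for an illustration.** Median survival is 10.6 to 12.5 years (section 5.1). Assumptions:
- exponential survival, applied from diagnosis although 5.1 gives it from onset;
- diagnosis dates uniform over 2009-2019, so potential follow-up runs from 1 to 11 years;
- no loss to follow-up;
- consent signed between August 2022 and October 2023;
- at a consent-only site, every survivor visits and signs.

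**Step 3: cohort with the waiver everywhere.** Hazard λ = ln 2/median. Probability of death by the cut-off: P = 1 - (e^(-λ) - e^(-11λ))/(10λ). Person-years per patient: P/λ.

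| Median (years) | λ | P | P/λ | Deaths in 170 |
|---|---|---|---|---|
| 10.6 | 0.0654 | 0.312 | 4.78 | 53 |
| 12.5 | 0.0555 | 0.274 | 4.94 | 47 |

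**Step 4: consent-only sites.** The fraction still alive at consent is q = 0.58 to 0.54 (median 10.6) or 0.63 to 0.59 (median 12.5), for consent in August 2022 to October 2023. Mean follow-up among these survivors is m = 5.46 or 5.54 years. Per source patient this is s = q·m = 3.15 to 2.92, or 3.47 to 3.25 years. A further 10% to 15% of patients die between the cut-off and the consent window, and their TE history and person-time are lost as well.

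**Step 5: pooled rate when a share w is consent-only.**
- w as a share of enrolled patients: (1-w)P / [(1-w)P/λ + w·m]
- w as a share of source patients: the same, with s in place of m

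Worked case, median 10.6, w = 0.20, enrolled: 0.8 × 0.3124 = 0.2499 deaths over 0.8 × 4.778 + 0.2 × 5.459 = 4.914 person-years. That is 5.09 per 100 person-years against a true 6.54, or -22%.

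| w | Bias, share of enrolled | Bias, share of source patients |
|---|---|---|
| 10% | about -11% | about -7% |
| 20% | about -22% | about -14% |
| 33% | about -36% | about -25% |

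Over both medians and both consent dates, the enrolled column moves by less than one percentage point. The source column runs from -6% to -7%, -13% to -15% and -23% to -26%.

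**Step 6: refusals at waiver sites.** If a fraction r of living attenders refuse, the rate becomes P/(P/λ - r·s). When every living patient attends, r = 10% gives about +7% (6.5% to 7.6%) and r = 20% gives about +14% to +16%. These are upper bounds, because living non-visitors enter under the waiver and cannot refuse. Multiplying r·s by the attending share gives about +5% and +10% if 70% attend, and about +3% and +7% if half attend.

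**The case against.** The strongest reply is that the waiver route is the plan everywhere. Section 8.2 says the waiver will be requested, the log for waiver patients is foreseen in all countries, 7.1 disregards vital status and 8.4 expects every consecutive eligible patient. On this view 2.2 and 14.2 are merely incomplete, and no passage says that a consent-only site exists. That stands as far as it goes: zero deaths is what follows a refusal or a literal reading of 14.2, not the intended state. But a request is not a grant, ethics submissions are made country by country, and the protocol has no rule for the refused case.

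A reader might infer that living patients can enter only by consent. They cannot be described so: the waiver also covers living patients who are lost to follow-up or did not visit. The consent-only route applies to those who attend, or to sites without the waiver.

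A reader might also infer that the primary TE rate is shown to be biased. Fatal TEs before the cut-off do drop out at a consent-only site, but survivors still contribute TEs and person-time is lost too. Neither direction nor size has been established.

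It is fair to say that entry-route tables and sensitivity analyses often sit in an SAP, which is not shown here. The contradiction between sections and the pooling rule in 13.3 are in the protocol itself. Finally, 8.2 lets a legally acceptable representative sign. Whether this can serve for a deceased patient is not stated.

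**Conclusion.** The concern holds in this form: where the waiver is not granted or not used, a site contributes person-time and no deaths, and the protocol pools it without a rule. The date logic needs no assumption. The contradiction of 2.2 and 14.2 with the Synopsis, 7.1 and 8.2 is plain from the text.

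The size is conditional. For consent-only shares of 10% to 33%, mortality is under-estimated by about 11% to 36% if these are shares of enrolled patients, or about 7% to 25% if shares of source patients. This rests on the survival model, uniform diagnosis dates and no loss to follow-up, and above all on a share that the protocol does not give. Refusals at waiver sites push the rate up, by at most about 7% to 16% for 10% to 20% refusal. Because the two biases have opposite signs, a pooled figure cannot show which one dominates. The figures are ranges and not a forecast.

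**What to change.** 1. **Sections 2.2 and 14.2:** add the waiver exception in the terms of 8.2, and bring the Synopsis and 8.2 to one wording.
2. **Sections 13.3 and 13.4:** estimate mortality, overall survival and cause-specific mortality from sites or countries where the waiver was granted. Give the TE rate with and without consent-only sites.
3. **Section 10.3.1:** record entry route as a study variable (consent, waiver-deceased, waiver-lost, waiver-no visit). The listed variables do not include it. It must be captured before the waiver log is destroyed at database lock.
4. **Section 13.2:** tabulate entry route per site, with an aggregate count of refusals.

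A bound that adds refusers as alive at 1 January 2020 should not be attempted: it needs at least their diagnosis dates, which are data from people who declined.

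The cost is some wording, one eCRF field and one table. The price in precision is fewer patients in the mortality analyses if some sites lack the waiver.
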